Part A is a dose-ranging, randomized, placebo-controlled, double-blind study designed to evaluate the safety and efficacy of tezepelumab as monotherapy in subjects with moderate-to-severe AD. Following the screening period, eligible subjects will be randomized 1:1:1:1 to receive 420 mg SC Q2W, 280 mg SC Q2W, 210 mg SC Q4W, or placebo. All subjects will receive a 420 mg SC dose (investigational product or placebo) as the first dose. Subjects will then receive the appropriate dose of investigational product at the week 2 visit, depending on which treatment group they are randomized to. Depending on if they are randomized to Q2W or Q4W dosing, the dose at week 2 could be placebo or tezepelumab. Non-responders are defined as those subjects who have not achieved at least a 50% improvement in EASI at week 16 compared to baseline (day 1). Subjects who are determined to be non-responders in Part A will receive tezepelumab 420 mg SC Q2W for the remainder of the study, beginning with the

week 18 dose. The randomized treatment assignments for the non-responders will remain blinded until the end of study.

Part B is a randomized, placebo-controlled, double-blind study designed to evaluate the safety and efficacy of tezepelumab when administered with moderate class TCS in adults with moderate-to-severe AD. Enrollment of subjects in Part B of the study will only commence if there is a result of “not futile” for the first interim analysis in Part A and Part A has completed enrollment of 240 patients. Following the screening period, eligible subjects will be randomized 2:1 to receive 420 mg SC Q2W or placebo; both groups in Part B will be allowed to use TCS after the day 1 visit. Non-responders in Part B will not be switched to 420 mg SC Q2W at week 18 and will remain on their initial dose for the duration of the study.

The overall study design is described by a study schema in [Section 2.1](#). The endpoints are defined in [Section 4.1](#).

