Depending on whether subjects are randomized to Q2W or Q4W dosing, the dose at week 2, **week 6, week 10 and so on**, could be placebo or tezepelumab. Non-responders are defined as those subjects who have not achieved at least a 50% improvement in EASI at week 16 compared to baseline (day 1). Subjects who are determined to be non-responders in Part A will receive tezepelumab 420 mg SC Q2W for the remainder of the study, beginning with the week 18 dose. The randomized treatment assignments for the non-responders will remain blinded until the end of study.

Part B is a randomized, placebo-controlled, double-blind **proof-of-concept** study designed to evaluate the safety and efficacy of tezepelumab when administered with moderate class TCS in adults with moderate-to-severe AD. Enrollment of subjects in Part B of the study will only commence if there is a result of “not futile” for the first interim analysis in Part A **and Part A has completed enrollment of 240 subjects**. Following the screening period, eligible subjects will be randomized 2:1 to receive 420 mg SC

Q2W or placebo; both groups in Part B will be allowed to use TCS after the day 1 visit. Non-responders in Part B will not be switched to 420 mg SC Q2W at week 18 and will remain on their initial dose for the duration of the study.

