#### Actual treatment received

##### *Part A:*

For Part A of the study, actual treatment will be defined as follows:

- If a subject either a) did not need to switch to tezepelumab 420 mg during the study, or b) should have switched to tezepelumab 420 mg but did not successfully do so, then the subject is considered a non-switcher. The subject's actual treatment received is defined below:
  - from day 1 until EOS for safety analysis of Day 1 to EOS (For safety analysis of Day 1 to week 16, use from day 1 until the day before the next dosing date after week 16 dose),
    - If a subject receives placebo only, the actual treatment will be defined as placebo
    - If a subject receives two or more doses of tezepelumab, the actual treatment will be defined as the highest dose of tezepelumab the subject receives since the date of the second IP (inclusive)
    - If a subject receives only one dose of tezepelumab, the actual treatment will be defined as the dose of tezepelumab the subject receives
- If a subject should have switched to tezepelumab 420 mg during the study and received a switching dose, then,
  - From day 1 until the day before the switch,
    - If a subject receives placebo only throughout this period, the actual treatment will be defined as placebo
    - If a subject receives two or more doses of tezepelumab during this period, the actual treatment will be defined as the highest dose of tezepelumab the subject receives since the date of the second IP (inclusive) until the day prior to the switch
    - If a subject receives only one dose of tezepelumab during this period, the actual treatment will be defined as the dose of tezepelumab the subject receives
  - From the date of switch until EOS,
    - If a subject receives at least one dose of tezepelumab 420 mg during this period, the actual treatment will be defined as tezepelumab 420 mg

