### Switching Date

**If a subject is determined as non-responder at week 16 in Part A as specified by the eCRF, the Switching Date of this subject will be defined as the date that the subject takes the first dose of tezepelumab 420 mg SC Q2W after week 16 in Part A.**

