#### **8.3.2 Missing Post-baseline Evaluation**

Refer to [Section 9.5.1.1](#) for handling of missing data for primary estimands defined in [Section 2.1](#).

**Secondary and exploratory endpoints will be included in descriptive summaries as observed without imputation for missing data. In analyses of secondary/exploratory endpoints involving statistical models detailed in [Section 9.5.2](#) and [Section 9.5.3](#), where endpoints cannot be derived due to missing IGA or EASI assessments, the missing binary endpoints (IGA 0/1, EASI50, EASI75,**

**EASI90) will be imputed using non-responder imputation (NRI). Missing binary endpoints that are not derived from IGA or EASI data (eg, Pruritus NRS  $\geq 2$ ) and missing continuous endpoints will not be imputed unless otherwise specified.**

Missing post-baseline safety data will not be imputed.

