**Additional characteristics may be considered if scientific interest arises.**

**Medical history and AD history will be summarized by treatment group and for all subjects combined.**

## **9.5 Efficacy Analyses**

The multiplicity for analyses of primary estimands will be adjusted for tezepelumab 420 mg vs. placebo and 280 mg vs. placebo comparison using the method described in [Section 9.5.1.1](#). **For sensitivity analyses, subgroup analyses of primary estimands, and analyses of secondary/exploratory endpoints in Part A and B, significance testing, if performed, will be considered descriptive at a level of 0.05 (2-sided) with nominal p-values without adjustment for multiplicity.**

**When modeling odds ratio based on logistic regression in analyses described in [Section 9.5.1](#), [Section 9.5.2](#) and [Section 9.5.3](#), in case of sparse data in one or more particular treatment arm that results in convergence issues, logistic regression model adjusted by dichotomized baseline score ( $\leq$ median,  $>$ median) will be used. Odds ratio and associated 95% CI and p-value will be reported.**

**The following descriptive summaries will be provided by treatment at available time points using FAS and observed cases unless otherwise specified**

- **Categorical efficacy endpoints: frequency/percentage.**
- **Continuous efficacy endpoints and associated changes from baseline: mean, standard deviation, median, 1st quartile, 3rd quartile, minimum, and maximum.**

**The above analyses will be performed using FAS-Part A by truncating the observations collected after switching to 420 mg SC Q2W for EASI-50 non-responders, and will be repeated using Switcher Analysis Set.**

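### Part A response percentages at weeks 24, 36 and 52 drop switched week-16 non-responders from a full-analysis-set denominator, inflating every arm's rate and distorting the arm contrast in a direction that cannot be predicted

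*SAP*

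**What the plan says.** The switch rule is in Protocol 5.1: "Non-responders are defined as those subjects who have not achieved at least a 50% improvement in EASI at week 16", compared with day 1. SAP 3.1 repeats the consequence: "Subjects who are determined to be non-responders in Part A will receive tezepelumab 420 mg SC Q2W for the remainder of the study", starting with the week 18 dose. It applies in all four arms, including the arm already on 420 mg Q2W.

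The table rule is in SAP 9.5: "The following descriptive summaries will be provided by treatment at available time points using FAS and observed cases unless otherwise specified". Categorical endpoints get frequency and percentage. For Part A these summaries use the full analysis set "by truncating the observations collected after switching to 420 mg SC Q2W for EASI-50 non-responders", and are repeated in the Switcher Analysis Set. SAP 8.3.2 adds: "Secondary and exploratory endpoints will be included in descriptive summaries as observed without imputation for missing data". SAP 6.1 defines the Part A full analysis set as all randomised subjects.

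For model-based analyses of IGA 0/1 and EASI 50/75/90, the same section 8.3.2 applies non-responder imputation when an IGA or EASI assessment is missing. SAP 9.5.3.1 specifies logistic models for these endpoints at weeks 24, 36 and 52.

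Two rules limit who is cut:
- In SAP 5.2, looking only at doses later than week 16, "the Switching Date of this subject will be defined as the date that the subject takes the first dose of tezepelumab 420 mg SC Q2W", so a subject with no switching dose has nothing to truncate. SAP 5.1 (actual treatment, a safety definition) agrees: a subject who "should have switched to tezepelumab 420 mg but did not successfully do so, then the subject is considered a non-switcher".
- SAP 5.5 and 5.6 derive the binary endpoint as 0, not missing, once TCS/TCI rescue has been used from day 29.

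**The concern.** Truncation, observed cases and no imputation together mean that a switched, non-rescued subject is neither a success nor a failure after week 16. The subject leaves both numerator and denominator. EASI and IGA are next scheduled at week 24 (Protocol Table 2-1), so every later by-arm percentage is affected. Who remains is decided by a post-randomisation outcome that the treatment is meant to change, yet the table is headed as the full analysis set.

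A reader would see the placebo rate jump between week 16 and week 24 with no change in anyone's skin, and would compare groups that are no longer the randomised ones. EASI 50 is the plainest case: the table selects on week-16 EASI 50 and then reports EASI 50. The same selection acts on the truncated means and changes from baseline.

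**Working it through.** **Inputs from the documents** (SAP 3.2): 60 subjects per arm; EASI 75 of 15% on placebo (9/60) and 50% on 420 mg Q2W (30/60); IGA 0/1 of 10% (6/60) and 40% (24/60). SAP 5.4 gives an odds ratio of 5.67 for EASI 75, which reproduces: (30/30) / (9/51) = 5.67. The planned differences are 35 points for EASI 75 and 30 points for IGA 0/1. The documents state no rates for weeks 24 to 52.

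**Assumptions:** the week-16 EASI 50 rate e (not in the documents; 20–50% on placebo, 55–80% on 420 mg); the share r of EASI 50 non-responders who took TCS/TCI rescue and so stay in as 0; week-16 status persists; every EASI 75 or IGA 0/1 responder is also an EASI 50 responder; every non-responder switches; no other missing data.

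**Formula:** printed rate = p / [e + r(1 − e)], where p is the rate over all randomised subjects. The divisor is below 1 whenever e and r are below 1, so every arm's rate is inflated relative to counting switchers as non-responders.

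**EASI 75 with r = 0** (over all randomised: 15% vs 50%, 35 points, odds ratio 5.67):

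| Assumed EASI 50, placebo / 420 mg | Placebo prints | 420 mg prints | Difference (points) | Odds ratio |
|---|---|---|---|---|
| 20% / 80% | 9/12 = 75.0% | 30/48 = 62.5% | −12.5 | 0.56 |
| 25% / 65% | 9/15 = 60.0% | 30/39 = 76.9% | 16.9 | 2.22 |
| 30% / 65% | 9/18 = 50.0% | 30/39 = 76.9% | 26.9 | 3.33 |
| 40% / 65% | 9/24 = 37.5% | 30/39 = 76.9% | 39.4 | 5.56 |
| 50% / 65% | 9/30 = 30.0% | 30/39 = 76.9% | 46.9 | 7.78 |
| 50% / 55% | 9/30 = 30.0% | 30/33 = 90.9% | 60.9 | 23.33 |

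The first and last rows are the extremes of the assumed grid for the difference. The placebo denominator is 12 to 30 instead of 60.

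**IGA 0/1 with r = 0** (planned difference 30 points): 25%/65% gives 6/15 = 40.0% vs 24/39 = 61.5%, 21.5 points; 40%/65% gives 6/24 = 25.0% vs 61.5%, 36.5 points. The grid runs from 0 to 52.7 points.

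**EASI 50 with r = 0:** e/e = 100% in every arm, so the difference is 0 whatever the true rates are. At 25%, 30% or 40% vs 65% the true difference is 40, 35 or 25 points.

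**With rescue, r = 0.25 in both arms, at 25%/65%:** the divisors are 0.25 + 0.25 × 0.75 = 0.4375 and 0.65 + 0.25 × 0.35 = 0.7375.
- EASI 75: 0.15/0.4375 = 34.3% vs 0.50/0.7375 = 67.8%, 33.5 points.
- IGA 0/1: 22.9% vs 54.2%, 31.4 points before rounding.
- EASI 50: 57.1% vs 88.1%, 31.0 points against a true 40.

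Both arms are still inflated, but the EASI 75 and IGA 0/1 differences end close to their planned values.

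**The case against.** The strongest reply is that little of importance hangs on these tables. They are exploratory and descriptive, any p-values are nominal, and SAP 9.5.3.1 takes the week 24, 36 and 52 treatment effect from logistic models and MMRM. Switched subjects do not vanish from the report: the summaries are repeated in the Switcher Analysis Set, their IGA 0/1 and EASI 75 rates are given by randomised arm, and SAP 9.2 counts them in disposition. This stands and limits the scope. It does not cure the problem, because neither summary gives a rate over all randomised subjects. (SAP 6.6, where study-specific sets are listed, is not in the text available, so the Switcher Analysis Set definition was not checked.)

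A reader might infer that the later rates are computed only in week-16 EASI 50 responders. The documents do not support that. Non-responders without a switching dose stay in, including those taken off study treatment who still attend visits (Protocol 7.1.5). TCS/TCI-rescued switchers may stay in as 0 under SAP 5.5 and 5.6; the SAP does not say whether truncation removes that derived 0.

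A reader might also infer that the arm contrast must collapse. That follows only for EASI 50, and only under persistence with no non-responder left in the table. For EASI 75 and IGA 0/1 the difference can go either way, as the table shows.

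Finally, a conflict between tables and logistic models is possible but not established. The truncation sentence in SAP 9.5.3.1 follows the MMRM text and is not stated for the logistic models, and the SAP does not say whether collected but truncated assessments count as missing for imputation. That is a point to settle, not a proven contradiction.

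**Conclusion.** The concern holds for the exploratory Part A descriptive tables after week 16. As written, the plan reports percentages conditional on a post-randomisation outcome under a label that means all randomised subjects. Relative to a denominator that keeps switchers as non-responders, the rates are inflated in every arm where a switcher is dropped.

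Under persistence with no rescued switchers, EASI 50 prints as 100% in every arm, and placebo EASI 75 prints as 30–75% instead of 15% for assumed placebo EASI 50 rates of 50–20%. The EASI 75 difference ranges from −12.5 to +60.9 points across the assumed rates, against 35 planned, so the direction of the distortion cannot be stated in advance. Rescue use reduces the inflation by an amount the documents do not allow one to estimate.

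The week-16 primary analysis and the week-16 secondary responder analyses precede the switch and are unaffected. The change is worth making because it is cheap and alters the printed rates, not because a main conclusion is at risk.

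**What to change.** In SAP 9.5 and 8.3.2, for Part A by-arm summaries of IGA 0/1 and EASI 50/75/90 after week 16:

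- Report rates over all randomised subjects, counting week-16 EASI 50 non-responders who switch as non-responders from the switch on. Use the same rule in all four arms, including 420 mg Q2W. Exempting that arm would let its week-16 failures gain late responses while failures elsewhere are fixed at zero.
- Show the observed-case rates beside them, with n.
- If the 420 mg arm's data on its unchanged regimen are of interest, give them as a separate, labelled summary. The Switching Date definition, read literally, truncates those data too.
- State that TCS/TCI-rescued switchers count as 0.
- State that the same rule applies to the logistic models in 9.5.3.1, so that tables and odds ratios agree.
- Label truncated means and changes from baseline as conditional on not having switched (mainly week-16 EASI 50 responders).

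The cost is SAP wording and modest re-programming, with no new data. Rates after week 16 will look lower in every arm.

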### **9.5.1 Analyses of Primary Efficacy Endpoint(s)**

#### **9.5.1.1 Primary Analysis of the Primary Endpoints**

[figure not shown]
The primary analysis of the primary estimands as defined in [Section 2.1](#) will be performed using the FAS – Part A. Primary endpoints are defined in [Section 5.5](#). **Where an endpoint cannot be derived due to missing IGA or EASI assessments, a patient will be assumed not to have achieved the outcome, that is, Non-Responder Imputation (NRI).**

Treatment effect **for IGA 0/1 at week 16** will be tested using a logistic regression model with baseline IGA as covariate. **Similarly, treatment effect for EASI 75 at week 16 will**

**be tested using a logistic regression model with baseline EASI as covariate.** From **each** model, odds ratio and 95% CIs will be reported, comparing each tezepelumab dose group to placebo.

To control the family-wise type 1 error rate at 0.05 (**2-sided**) for the multiple comparisons of 420 mg vs. placebo and 280 mg vs. placebo, the hypotheses **described in Section 2.2** will be tested using a Bonferroni-based gatekeeping chain procedure (**Dmitrienko 2013**) as shown in [Figure 9-1](#). This procedure will split alpha of 0.05 equally to test in parallel tezepelumab 420 mg SC Q2W versus placebo and tezepelumab 280 mg SC Q2W versus placebo for IGA 0/1 and EASI 75 sequentially within each parallel **dose** path. If one of the parallel **dose** paths rejects **the 2** hypotheses sequentially, and the other **dose** path has at least one hypothesis not rejected, then the unspent  $\alpha$  of 0.025 from the successful path will be propagated to the **unsuccessful dose path** to retest the 2 hypotheses sequentially at a level of 0.05.

Figure 9-1. Alpha Split Between Two Doses of Interest

In addition, analysis of primary endpoints may be considered using mFAS-Part A as a supporting analysis to examine the impact of COVID-19 2020 outbreak on outcomes without multiplicity adjustment.

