10.3.2 Methods of Analyses

10.3.2.1 General Considerations

Subject disposition, demographics, and baseline disease characteristics will be summarized descriptively by randomized treatment group. For categorical endpoints, the descriptive statistics will contain frequency and percentage. For continuous endpoints, the descriptive statistics will include the number of observations, mean, standard error, standard deviation, median, first quartile, third quartile, minimum, and maximum.

For Part A, the treatment effect for the primary analysis of the primary endpoints will be tested using a Bonferonni-based gatekeeping procedure to control the family-wise 2-sided type I error rate at 0.05. The procedure splits the α of 0.05 equally to test in parallel tezepelumab 420 mg SC Q2W versus placebo, and tezepelumab 280 mg SC Q2W versus placebo for IGA 0/1 and EASI 75 sequentially within each parallel path. If one of the parallel paths rejects the 2 hypotheses sequentially, and the other path has at least 1 hypothesis not rejected, then the unspent α of 0.025 from the successful path will be propagated to the unsuccessful path to retest the 2 hypotheses sequentially at a level of 0.05. This procedure is illustrated in [Figure 10-1](#).

Figure 10-1. Alpha Split Between Two Doses of Interest

For all other endpoints in Part A and B, significance testing, if performed, will be considered descriptive.

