**Specifically, the four primary hypotheses are as follows:**

#### **IGA 0/1 at week 16**

**H01: Odds ratio of IGA 0/1 at week 16 between tezepelumab 420 mg SC Q2W and placebo = 1**

**Vs.**

**H11: Odds ratio of IGA 0/1 at week 16 between tezepelumab 420 mg SC Q2W and placebo ≠ 1**

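### When all four primary hypotheses are rejected, the 0.05 is assigned to nothing; 210 mg Q4W could be tested last at no cost to the higher doses

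*SAP*

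**What the plan says.** Part A randomizes 240 subjects 1:1:1:1 to 420 mg Q2W, 280 mg Q2W, 210 mg Q4W or placebo. Protocol 3.1 says the three regimens are meant to establish exposure-response and help dose selection for later studies.

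Protocol 10.3.2.1 sets out to "control the family-wise 2-sided type I error rate at 0.05". SAP 2.2 states that "the four primary hypotheses are as follows", and all four concern 420 mg or 280 mg, each on IGA 0/1 and EASI 75 at week 16. The four primary estimands in SAP 2.1 match them.

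Protocol 10.3.2.1 and SAP 9.5.1.1 describe the same chain. In the SAP's words, "This procedure will split alpha of 0.05 equally to test in parallel tezepelumab 420 mg SC Q2W versus placebo", with 280 mg Q2W versus placebo as the other path. Each dose path receives 0.025 and tests IGA 0/1, then EASI 75. If one path succeeds on both and the other does not, the 0.025 passes to the unsuccessful path "to retest the 2 hypotheses sequentially at a level of 0.05". Nothing is said about what follows when both paths succeed. The figure is not reproduced in the text available, but its caption is "Figure 9-1. Alpha Split Between Two Doses of Interest".

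For 210 mg, SAP 9.5.1.1 provides odds ratios and 95% CIs "comparing each tezepelumab dose group to placebo". Protocol 10.3.2.2 adds response percentages and differences with 95% CIs.

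**The concern.** In a dose-ranging trial, once both higher regimens have succeeded, a natural next question is whether the lowest one also works. At that point the full 0.05 is unspent, and the plan has no hypothesis, alpha or estimand for 210 mg. A quarter of Part A can therefore support no conclusion inside the controlled family.

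The status of the 210 mg comparison is also left open. The Protocol 10.3.2.1 sentence "For all other endpoints in Part A and B, significance testing, if performed, will be considered descriptive" is about other endpoints, whereas 210 mg is compared on the primary ones. SAP 9.5 restricts multiplicity adjustment to 420 mg and 280 mg. It labels sensitivity, subgroup and secondary/exploratory analyses as descriptive, and 210 mg versus placebo on IGA 0/1 and EASI 75 is none of these. A small nominal p-value for 210 mg could be read in different ways after the fact.

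**Working it through.** **1. Inputs.** Protocol 10.1 and SAP 3.2 give about 60 per arm, 10% dropout, IGA 0/1 rates of 10% (placebo) and 40% (420 mg), EASI 75 rates of 15% and 50%, and a 2-sided chi-square test at 0.025. They give no rates for 280 mg or 210 mg.

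**2. The plan's own power figure.** Evaluable n = 60 × 0.9 = 54 per arm. Power = Φ{(d√n − z√(2p̄q̄)) / √(p₁q₁ + p₂q₂)}, with z = 2.241.

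- IGA 0/1: (0.30 × 7.348 − 2.241 × √0.375) / √0.33 = (2.205 − 1.373) / 0.574 = 1.45, power 92.6%.
- EASI 75: (0.35 × 7.348 − 2.241 × √0.43875) / √0.3775 = (2.572 − 1.485) / 0.614 = 1.77, power 96.2%.

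The stated minimum of 85% holds.

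**3. Alpha bookkeeping.** 0.05 / 2 = 0.025 per path. After both paths succeed, 0.025 + 0.025 = 0.05 remains, with no destination in the text.

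**4. Validity of a last step.** Test 210 mg on IGA 0/1, then EASI 75, each at 0.05, only if H01-H04 are all rejected.

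- If any of H01-H04 is true, a false 210 mg rejection requires that this true null has already been rejected. The trial is then already counted as an error under the existing chain, so no new error is added.
- If all of H01-H04 are false, 210 mg is tested in fixed order at 0.05, and the chance of any false rejection is at most 0.05.
- No 420 mg or 280 mg test comes after the new step, so their decisions and power are unchanged.

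Simulation agrees (200,000 trials per scenario, 54 per arm, latent correlation between endpoints 0.5 and 0.8):

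| True state | Family-wise error, current | With 210 mg last |
|---|---|---|
| All doses null | 0.038 | 0.038 |
| 280 mg and 210 mg null | 0.044-0.045 | 0.044-0.045 |
| Only 210 mg null, planning rates for the others | 0 | 0.040 |
| Only 210 mg null, other doses near-certain to succeed | 0 | 0.049-0.051 |

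The last row is the 0.05 bound within simulation error.

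**5. Size of the gain.** Here n = 60 per arm, all rates are multiplied by 0.9 (10% dropouts counted as non-responders) and the correlation is 0.8. Placebo and 420 mg are at the planning rates; the 280 mg and 210 mg rates are assumptions, shown as IGA 0/1 / EASI 75. Futility stopping is not modelled because the rule is blacked out.

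| 280 mg | 210 mg | All four rejected | 210 mg IGA 0/1 also rejected | Both 210 mg rejected |
|---|---|---|---|---|
| 40/50% | 30/40% | 0.90 | 0.70 | 0.64 |
| 35/45% | 25/35% | 0.81 | 0.47-0.48 | 0.40 |
| 30/40% | 20/30% | 0.65 | 0.25 | 0.18 |
| 25/35% | 20/30% | 0.42-0.43 | 0.19 | 0.15 |

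The last three columns are proportions of all trials. Small ranges reflect repeat runs. In the first row, given that the step is reached, 0.70 / 0.90 = 78% reject 210 mg IGA 0/1.

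The 54-per-arm simulation gives a similar picture. With 280 mg at the 420 mg rates, the step is reached in 0.90-0.91, and 210 mg IGA 0/1 is rejected in 0.89, 0.72, 0.52-0.53 and 0.30 of trials at a 210 mg response of 40%, 30%, 25% and 20%.

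**The case against.** The best defence is that the omission is deliberate. Estimands, hypotheses, the multiplicity sentence in SAP 9.5 and the figure caption all name two doses, consistently. A sponsor may choose which doses carry formal claims. Dose selection is said to rest on exposure-response, which is a matter of estimation across arms rather than of a pairwise test. The 210 mg odds ratio and CI are reported anyway, so the extra test adds formal status and no new data.

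Much of this stands. A reader might infer that the procedure is faulty; it is not, because the family-wise error of the four hypotheses is controlled and the stated power holds. A reader might also infer that the plan offers no inference at all on 210 mg; in fact a nominal 95% CI is provided, and what is missing is family-wise control. Nor does the Protocol 10.3.2.1 sentence on other endpoints settle the matter, since it does not mention this comparison.

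The defence does not, however, identify a statistical downside to the added step. The exposure-response analysis is conditional: Protocol 7.3.2 speaks of it only if performed, and SAP 9.7.1 only as needed. Formal status would change what the trial may conclude about its lowest regimen.

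**Conclusion.** The point holds as an optional improvement. After four rejections 0.05 is left without a destination, and using it for 210 mg Q4W costs nothing in type I error or in power for 420 mg and 280 mg.

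The benefit is conditional. The favourable figures (about 90% reaching the step, about 70% rejecting 210 mg IGA 0/1) require 280 mg to perform like 420 mg and 210 mg to reach a 30% response, and the documents support neither assumption. They should not be read as the expected yield. Under the graded dose responses tried, the step is reached in about 42-81% of trials and 210 mg IGA 0/1 is rejected in about 19-47%. If either higher-dose path is incomplete, 210 mg remains untested. The reading of the chain rests on the text and the figure caption, since the figure is not shown.

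**What to change.** Before unblinding, add two hypotheses: 210 mg SC Q4W versus placebo for IGA 0/1 at 2-sided 0.05 and, if rejected, for EASI 75 at 2-sided 0.05, both only when H01-H04 have all been rejected.

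The edits go somewhat beyond one sentence:

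- SAP 2.1: two further primary estimands.
- SAP 2.2: the hypothesis list.
- SAP 9.5: the multiplicity sentence.
- SAP 9.5.1.1 and Figure 9-1: the added step.
- Either Protocol 10.3.2.1 and Figure 10-1 by amendment (with the matching synopsis text), or an entry in SAP section 10 recording the change from the protocol.

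No extra subjects, assessments or models are needed, since the 210 mg odds ratios come from the models already planned. If the sponsor prefers to keep two doses in the family, one sentence in SAP 9.5 stating that 210 mg versus placebo on the primary endpoints is descriptive would at least close the gap in status.
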